14.2. Sample Size Justification

A total of approximately 50 eligible subjects will be enrolled into the study at this site. At least 40 subjects will complete this study. There have been no prior historical dispensing studies in presbyopes with the Test article to determine sample size. This is a pilot study and the sample size calculation was not based on any power analysis. The collected data will be used to design future trials.

Using the POWER procedure in SAS 9.4, below is the summary of sample size required based on the different assumptions of the true difference. Each study hypothesis is tested with at least 90% of statistical power and 2-sided type I error of 0.05.

- lens centration and lens movement

Actual Odds Ratio	Control Lens Proportion	# of eyes needed	Power
1.0	0.75	571	0.8
1.5	0.75	164	0.8
2.0	0.75	100	0.8

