2.3. Hypotheses

The following hypotheses will be tested throughout this investigation.

Primary Hypotheses:

1. After 6-8 days of wear in the optimized lenses, the proportion of lenses graded as being centered for the test lens will be non-inferior compared to the control lens. A non-inferiority margin of 0.67 odds ratio will be used.
2. After 6-8 days of wear in the optimized lenses, the proportion of lenses graded as having optimal lens movement in primary gaze for the test lens will be non-inferior compared to the control lens. A non-inferiority margin of 0.67 odds ratio will be used.

Secondary Hypothesis:

1. After 6-8 days of wear in the optimized lenses, the overall lens handling of the test lens system will be non-inferior compared to that of the control lens system. A non-inferiority margin of -5 CLUE points will be used.

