4. STUDY DESIGN AND RATIONALE

4.1. Description of Study Design

The clinical study is a randomized-controlled, single-masked, crossover clinical trial. There are two study treatments. A total of approximately 50 subjects will be enrolled with 40 (20 myopic and 20 hyperopic) eligible subjects targeted to complete the study. The first Test article will be dispensed for 3 ± 1 day and an optimization visit will occur. The final lens pair will be dispensed for 7 ± 1 day and the at the follow-up the final lens measurements will occur. Subjects will complete a 7 ± 3 days washout between each fitting. The second study lens will then be fit and follow the same sequence as the first lens.

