5. TEST ARTICLE ALLOCATION AND MASKING

5.1. Test Article Allocation

The study lenses will be worn in a bilateral and random fashion using a 2×2 crossover design with 2 lens types and 2 periods. Using a computer-generated randomization scheme provided by the study biostatistician, each subject will randomly be assigned to one of two unique sequences (Test/Control or Control/Test). Randomization will be stratified by site.

Permuted block randomization will be used to avoid bias in the assignment of subjects to treatment, and to enhance the validity of statistical comparisons across treatment groups. Each block will contain two different lens trial sequences.

The order of lens wear will be based on the randomization scheme assigned to the study site. The study site will follow the randomization scheme provided and will complete enrollment according to the randomization list and will not pre-select or assign subjects.

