14.5. Primary Analysis

Primary efficacy analysis:

The lens centration and lens movement outcomes will be converted to a binary response where 1= lens is centered or have optimal lens movement, and 0=otherwise.

The proportion of response ("1") will be analyzed using a generalized linear mixed model with a binary distribution and logit link function for all questions. Each model will include the experimental design factors: lens, period and lens by period interaction as fixed effects; and site and subject nested in site as random effects. Other baseline characteristics known to be important such as subject group (myope/hyperope), age, gender, and/or add power will be included as fixed covariates when appropriate. The covariance between residual errors from two eyes from the same subject at the same lens wearing period will be selected based on the finite-sample corrected Akaike's Information Criterion.⁶ Covariance structures considered may include: Homogenous compound symmetry (CS) and Unstructured covariance structure (UN). The structure that returns the lowest Akaike Information Criteria Corrected (AICC) will be selected as the structure that best fit the data.

Comparisons between the study lenses will be carried out using two-sided 95% confidence intervals of odds ratios (odds ratio calculated as Test / Control) for each individual question. Non-inferiority will be concluded if the lower limit is above 0.67. Superiority will be concluded if the lower limit is above 1.0.

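### Section 14.2 claims at least 90% power for each hypothesis, but its own table is computed at 80% and every row needs more eyes per lens (100 to 571) than the 80 that 40 completers supply

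*Combined protocol and SAP*

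**What the plan says.** Section 14.2 of the combined protocol and SAP plans for about 50 enrolled subjects and says "At least 40 subjects will complete this study". Section 4.1 gives the same target: "A total of approximately 50 subjects will be enrolled with 40 (20 myopic and 20 hyperopic) eligible subjects targeted to complete the study". Section 14.2 calls the study a pilot, says its size does not come from a power analysis, and says the data will serve the design of later trials.

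It then introduces a table made with the SAS POWER procedure: "below is the summary of sample size required based on the different assumptions of the true difference". The next sentence is "Each study hypothesis is tested with at least 90% of statistical power and 2-sided type I error of 0.05". The table covers lens centration and lens movement only:

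| True odds ratio | Control proportion | Eyes needed | Power |
|---|---|---|---|
| 1.0 | 0.75 | 571 | 0.8 |
| 1.5 | 0.75 | 164 | 0.8 |
| 2.0 | 0.75 | 100 | 0.8 |

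The column does not say whether the eyes are per lens or in total.

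On the design, section 5.1 specifies a 2×2 crossover: "The study lenses will be worn in a bilateral and random fashion". Section 14.5 concludes non-inferiority when the lower bound of the two-sided 95% interval for the odds ratio exceeds 0.67. It selects a structure for "The covariance between residual errors from two eyes from the same subject at the same lens wearing period". Section 14.1 places all analyses on the per-protocol population. For the secondary handling hypothesis, section 2.3 says: "A non-inferiority margin of -5 CLUE points will be used".

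**The concern.** The 90% sentence can be read in two ways. As the target power behind the table, it conflicts with the power column. As the power this trial will have, it needs a sample size to support it, and the planned one is below every row of the table.

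Two uses of the section are at stake. The protocol has formal non-inferiority and superiority rules, so a reader who believes the power is 90% will take a failure to show non-inferiority as stronger evidence against the test lens than it is. Someone planning a later trial could take 571, 164 or 100 as 90% sample sizes, or as totals over both lenses, and undersize that trial.

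**Working it through.** **Inputs.** Control proportion 0.75; true odds ratios 1.0, 1.5 and 2.0; power 0.8 (table, section 14.2); "2-sided type I error of 0.05" (section 14.2); margin 0.67 (section 2.3); 40 completers, both eyes, each subject wearing both lenses (sections 4.1, 5.1, 14.2). Eyes per lens = 40 × 2 = 80; if all 50 enrolled complete, 50 × 2 = 100.

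**1. Reproducing the table.** Use the pooled two-proportion test without continuity correction:

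n per group = [1.960·√(2p̄(1−p̄)) + z_power·√(p0(1−p0) + p1(1−p1))]² / (p1−p0)²

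Here p0 = 0.75 (odds 3), p̄ = (p0+p1)/2, and p1 has odds 3 × OR/margin. With the margin taken as 2/3, the odds are 4.5, 6.75 and 9, so p1 = 0.818, 0.871 and 0.900.

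| True OR | n per lens, 80% | Printed | n per lens, 90% |
|---|---|---|---|
| 1.0 | 570.5 → 571 | 571 | 763.2 → 764 |
| 1.5 | 163.6 → 164 | 164 | 218.5 → 219 |
| 2.0 | 99.5 → 100 | 100 | 132.8 → 133 |

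All three rows match at 80%, as counts per group. Totals over both lenses would be 1142, 328 and 200. The value 2/3 is inferred from the match; a margin of exactly 0.67 gives 584, 166 and 101.

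**2. Power of the planned sample by the same method.** Solve the formula for z_power at n = 80 and n = 100.

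| True OR | 80 eyes per lens | 100 eyes per lens |
|---|---|---|
| 1.0 | 18% | 21% |
| 1.5 | 50% | 59% |
| 2.0 | 71% | 80% |

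**3. Closer to the planned rule.** The table's method treats eyes as independent and lenses as separate groups. A log odds ratio approximation to the confidence-interval rule is

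power = Φ[ln(OR/0.67)/SE − 1.960], SE² = (1+ρ_eye)·(v0 + v1 − 2ρ_lens·√(v0·v1))/80, v = 1/(p(1−p)).

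Here p is 0.75 for control and, for the test lens at its true odds ratio, 0.750, 0.818 or 0.857. ρ_eye is the fellow-eye correlation and ρ_lens the correlation between a subject's means on the two lenses. The documents give neither, so the values below are assumptions.

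| ρ_eye, ρ_lens | OR 1.0 | OR 1.5 | OR 2.0 |
|---|---|---|---|
| 0, 0 | 19% | 55% | 76% |
| 0.8, 0 (lowest) | 13% | 34% | 51% |
| 0.5, 0.5 | 24% | 67% | 86% |
| 0, 0.7 (highest) | 52% | 96% | 99.7% |

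**4. Expected precision.** For an observed odds ratio of 1.0, independent eyes and unpaired lenses, SE = √(2/(80 × 0.1875)) = 0.365, so the 95% interval is exp(±1.960 × 0.365) = 0.49 to 2.05.

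**5. CLUE handling.** Section 14.2 gives no standard deviation. Take 40 completers, a true difference of 0, margin 5, one-sided 0.025 and a noncentral t with 38 df and noncentrality 5·√40/SD, where SD is that of the within-subject lens difference. Power reaches 90% only if SD is about 9.5 points or less. Assumed SDs of 10, 15 and 20 give 87%, 54% and 34%.

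**The case against.** The strongest reply is that the study is a declared pilot whose size was not derived from power. A reference table asking for more eyes than a pilot supplies is no error in itself. The 90% sentence introduces that table, so it is most naturally a mistyped target power rather than a claim about this trial. On that view the defect is one wrong number and a missing label.

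Most of this stands. The shortfall of 80 against 100 to 571 would be no defect without the 90% sentence, and the table's arithmetic is correct. But the pilot statement does not make the sentence true. Two sentences later the section attributes at least 90% power to every study hypothesis, including one for which it shows no calculation.

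A second reply is that 18%, 50% and 71% are not the power of the planned mixed model, because crossover pairing helps. That also stands in part. If one shared subject effect produced both correlations with an assumed intraclass correlation of 0.5 (ρ_eye = 0.5, ρ_lens = 2 × 0.5/1.5 = 0.67), the formula in step 3 gives about 34%, 83% and 96%. At odds ratios of 1.5 and 2.0 the documents therefore cannot settle the power either way. For equal lenses, 90% is out of reach throughout the range examined.

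Finally, the CLUE powers rest on assumed standard deviations. What the documents themselves show is only that no calculation was given.

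**Conclusion.** The concern holds. As a description of the table, the 90% sentence is wrong: the table is an 80% table, exact in all three rows, and 90% would take about a third more eyes per lens (764/571 = 1.34, 219/164 = 1.34, 133/100 = 1.33). As a statement about this trial it is unsupported. The 40 completers give 80 eyes per lens, and the table's own method, with independent eyes and unpaired lenses, does not reach 90% in any row even if all 50 enrolled subjects complete.

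The firm conclusion on achieved power is limited to equal lenses, where it stays at or below 52% for fellow-eye correlation 0 to 0.8 and between-lens correlation 0 to 0.7. At a true odds ratio of 1.5 or 2.0, 90% is possible under strong pairing that the protocol does not assume. For CLUE handling the claim has no stated basis. The correction should be made, but the planned sample size, analysis and decision rule do not depend on it.

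**What to change.** In section 14.2:

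- Delete the 90% sentence.
- Label the column as eyes needed per lens at 80% power.
- Keep the statement that this is a pilot whose size was not based on power.
- Add what 40 completers provide, in one of three forms: power by the table's method (18%, 50%, 71%), stating that eyes are treated as independent and lenses as unpaired; power under explicit eye and lens correlations; or the expected interval width (about 0.49 to 2.05 for an observed odds ratio of 1.0 with independent eyes and unpaired lenses).
- For CLUE handling, give the assumed standard deviation and resulting power, or say that none was calculated.

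This is a text change, with no added subjects and no change to the analysis. The only cost is a less favourable stated power.

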14.3. Analysis Populations

Safety Population:

All subjects who were administered any test article excluding subjects who drop out prior to administering any test article. At least one observation should be recorded.

Per-Protocol Population:

All subjects who have successfully completed all visits and did not substantially deviate from the protocol as determined by the trial cohort review committee prior to database hard lock (Per-Protocol Population). Justification of excluding subjects with protocol deviations in the Per-Protocol Population set will be documented in a memo to file.

Intent-to-Treat (ITT) Population:

All subjects regardless of actual treatment and subsequent withdrawal from study or deviation from protocol. At least one observation should be recorded.

14.4. Level of Statistical Significance

All planned analysis for this study will be conducted with an overall type I error rate of 5%.

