14.6. Secondary Analysis

Secondary efficacy analysis:

CLUE handling scores will be analyzed using a linear mixed model adjusting for baseline values as fixed covariates. The model will include the experimental design factors: lens, period and lens by period interaction as fixed effects. Other baseline characteristics known to be important such as subject group (myope/hyperope), age, gender, and/or add power will be included as fixed covariates when appropriate. The covariance between residual errors from the same subject across lens wearing periods will be selected based on the finite-sample corrected Akaike's Information Criterion.⁶ Covariance structures considered may include: Homogenous compound symmetry (CS) and Unstructured covariance structure (UN). The structure that returns the lowest Akaike Information Criteria Corrected (AICC) will be selected as the structure that best fit the data.

Comparisons between the Test lens and Control lens will be carried out using 95% confidence intervals constructed of least-square means (LSM) differences (Test minus Control) from the linear mixed model. The non-inferiority of the Test lens relative to the Control will be concluded if the lower confidence limit of LSM difference is above the non-inferiority margin -5. The superiority will be established if the lower confidence limit is above 0.

In all models, the Kenward and Roger method⁶ will be used for the calculation of the denominator of degrees of freedom.

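### Section 14.4 promises an overall 5% type I error, but three separate, ungated non-inferiority claims at one-sided 2.5% each can reach about 7.3% (bound 7.5%)

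*Combined protocol and SAP*

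**What the plan says.** Section 14.4 is a single sentence: "All planned analysis for this study will be conducted with an overall type I error rate of 5" percent. It does not state sidedness, and its scope is every planned analysis.

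Section 2.3 names three hypotheses, all of non-inferiority:

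- Primary 1, centration: "the proportion of lenses graded as being centered for the test lens will be non-inferior compared to the control lens", with an odds ratio margin of 0.67.
- Primary 2, movement: "the proportion of lenses graded as having optimal lens movement in primary gaze for the test lens will be non-inferior", with the same margin.
- Secondary, handling: "the overall lens handling of the test lens system will be non-inferior compared to that of the control lens system". For this one, "A non-inferiority margin of -5 CLUE points will be used".

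Section 14.2 sets the level hypothesis by hypothesis: "Each study hypothesis is tested with at least 90% of statistical power and 2-sided type I error of 0.05".

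Section 14.5 takes a two-sided 95% interval for the odds ratio of each primary outcome separately: "Non-inferiority will be concluded if the lower limit is above 0.67. Superiority will be concluded if the lower limit is above 1.0". In section 14.6, non-inferiority for the handling score "will be concluded if the lower confidence limit of LSM difference is above the non-inferiority margin -5", again from a 95% interval, and superiority if the limit is above 0. That rule does not refer to the primary results.

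No section gives a testing order, an alpha split, a gate from primary to secondary, or a rule that both primaries must succeed. Section 14.10 says the analysis follows the sections above it and points to no other document for such a rule.

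**The concern.** An overall error rate is a statement about the set of claims taken together. The decision rules treat the claims one at a time, each at its own full level. The primary and secondary labels rank the endpoints, but nothing in the plan turns that ranking into a condition. As written, handling non-inferiority can be concluded even if centration and movement both fail.

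A reader of 14.4 would take the three conclusions as jointly protected at 5%. How far they fall short depends on a word the section omits:

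- If the 5% is one-sided, the two primaries comply and the excess comes from the ungated handling claim.
- If it is two-sided, leaving 2.5% in the non-inferiority direction, the two primaries claimed separately already exceed it.

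**Working it through.** **Inputs.** Three non-inferiority tests (2.3). Each is decided by the lower limit of a 95% interval (14.5, 14.6), so one-sided α = 0.025 per test. Section 14.5 prints two-sided; 14.6 does not, and I take it from the two-sided 0.05 per hypothesis in 14.2. The promised total is 5% (14.4). The documents give no correlation between the endpoints, so a range is assumed below.

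**1. Can the 5% be reproduced?** Only by counting the two primaries and reading 5% as one-sided:

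- Bound: 2 × 0.025 = 0.050.
- Independent: 1 − 0.975² = 0.0494.

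**2. All three planned non-inferiority tests, each true effect at its margin:**

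- Bound under any dependence: 3 × 0.025 = 0.075.
- Independent: 1 − 0.975³ = 0.0731.

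**3. Allowing for correlation.** For normal test statistics with common correlation ρ and critical value 1.96,

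P(at least one of k false) = 1 − ∫ φ(u) · Φ((1.96 − √ρ·u)/√(1 − ρ))^k du.

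| Assumed ρ | Any of 3 | Any of 2 primaries |
|---|---|---|
| 0 | 7.31% | 4.94% |
| 0.3 | 6.83% | 4.76% |
| 0.5 | 6.27% | 4.54% |
| 0.7 | 5.46% | 4.17% |
| 0.9 | 4.18% | 3.52% |

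The three-test rate equals 5% at ρ = 0.785. If only the two primaries are correlated, at 0.9, and handling is independent, the rate is 1 − (1 − 0.0352) × 0.975 = 0.0593.

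**4. Does superiority add to this?** Not to the bound. For each endpoint, superiority is read from the same interval, so a superiority claim always carries the non-inferiority claim with it. If the true effect is at or below the margin, the chance of any false claim on that endpoint is at most 2.5%. If it lies between the margin and equality, only the superiority claim can be false, again with at most 2.5%. Three endpoints at 2.5% still give 7.5%.

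**5. Would a gate restore the promise?** Suppose handling is tested only if both primaries are non-inferior, and the primaries may still be claimed separately.

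- Both primaries truly inferior: a false handling claim needs false primary claims first, so the rate is that of the two primaries, at most 5.0% (4.94% if independent).
- One primary truly inferior: any false claim needs that primary's false claim, so at most 2.5%.
- Neither inferior: only handling can be falsely claimed, so at most 2.5%.

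A simulation with 2 million draws and ρ = 0 agrees. With all three at their margins it gives 0.0731 ungated and 0.0494 gated. Gated, it gives 0.0251 with one primary far above its margin and 0.0250 with both far above. If both primaries are also required for the fit claim, the maximum is 0.025.

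**The case against.** The strongest reply is that the word for overall in 14.4 is loose drafting for a common 5% level. That would agree with the per-hypothesis level in 14.2 and with the 95% intervals in 14.5 and 14.6. On that reading no analysis rule is wrong and one sentence needs correcting. This is fair as to what may have been intended, and it is why rewording is one of the two remedies. It does not make the printed sentence correct.

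Second, many plans do not hold secondary endpoints to familywise control, and without handling the primaries meet a one-sided 5%. That stands for the primaries. But 14.4 covers every planned analysis, and 2.3 lists handling among the hypotheses to be tested.

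Third, 7.3% is a corner case: all effects exactly at their margins and independent statistics. Centration and movement are graded in the same step on the same lenses (steps 3.10 and 6.10), so exact independence is an idealization. This is true, but the rate stays above 5% until the common correlation is close to 0.79, and 7.3% is itself not the ceiling, which is 7.5%.

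Fourth, the stakes are low. Section 14.2 calls the study a pilot not sized by a power analysis, with data meant for designing future trials. Its table asks for 571 eyes at a true odds ratio of 1.0 and 164 at 1.5, against about 40 completers, or 80 eyes. Few claims are likely to succeed, and a full testing hierarchy may be more than such a study needs. This lowers the weight of the point. It does not reduce the type I error of the rules or withdraw the stated rate.

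**Conclusion.** The concern holds. The overall 5% in 14.4 does not follow from the decision rules in 14.5 and 14.6. For the three non-inferiority claims the rate is 7.3% if the tests are independent and all effects are at their margins, with a strict bound of 7.5%. It is 6.8% to 5.5% for assumed common correlations of 0.3 to 0.7.

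The part of the plan that fails depends on the unstated sidedness. Against a one-sided 5%, only the ungated handling claim causes the excess. Against a one-sided 2.5%, the two primaries alone, at 4.9%, already exceed it. The result rests on reading the 14.6 interval as two-sided and on taking the scope of 14.4 as printed. Because this is a pilot, it is a correction that should be made rather than a threat to the study.

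**What to change.** Choose one of the following, before the database is locked.

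**(A) Keep an overall rate.** State its sidedness in 14.4, and test handling non-inferiority only if centration and movement are both non-inferior. This holds a one-sided 5%, with the primaries still claimed separately. If one-sided 2.5% is intended, also require both primaries to succeed before any fit claim is made. Test superiority afterwards in one strict fixed order that starts only once handling non-inferiority has succeeded, or label superiority as outside the overall rate. Opening primary superiority alongside handling non-inferiority would put up to three 2.5% tests in parallel and could return the rate to 7.3%.

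**(B) Drop the overall promise.** Reword 14.4 as a two-sided 5% level for each hypothesis, as in 14.2, and state that the overall one-sided rate can reach about 7.5%. This is the lighter change and is adequate for a pilot.

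Either option takes one to three sentences in 14.4 to 14.6 and leaves the intervals, margins and sample size as they are. The price of (A) is that no formal handling claim can be made if either primary fails. The price of (B) is that the report cannot claim joint 5% control.
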